3.0 STUDY OBJECTIVES

- 1) To assess breast cancer survivors with chronic pain for the presence and degree of pain centralization
- (2) To identify predictors of response to the primarily centrally-acting analgesic duloxetine in breast cancer survivors with chronic treatment-emergent pain.

4.0 RESEARCH DESIGN AND METHODS

The randomized, placebo-controlled, cross-over design was originally chosen because it enables each individual who enters the study to either support or refute our primary mechanistic hypothesis. However there were significant difficulties with recruitment of patients to the trial as originally

designed, in part because a high proportion of breast cancer survivors with chronic pain require an antidepressant/anxiolytic medication and are reluctant to be on placebo for 7 weeks. Therefore the study team decided to revise the study design and convert it to a single-arm open label trial. The study objectives are unchanged. The placebo effect should be equally distributed across participants with and without centralized pain, and therefore should not influence the assessment of predictors of response to duloxetine. The new design more accurately reflect real world decisions that face providers and patients when deciding whether to switch from one antidepressant medication to another based on the potential benefit-risk profile.

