5.0 OVERALL STUDY DESIGN AND PLAN: DESCRIPTION

5.1 Overview of Study Design

This is a single-center, single-arm, open-label study conducted at the University of Michigan's Chronic Pain and Fatigue Research Center (Figure 4). Patients with stage 0-III breast cancer who have chronic pain that developed or worsened since breast cancer diagnosis and whose worst pain is rated at least 5 on a 10 point Likert-type scale and who meet the other inclusion and exclusion criteria outlined in Sections 5.4 and 5.5 will be eligible to enroll in the study.

Patients with chronic pain (cases) who qualify for the study at Screening will begin a 1- to 4-week washout period (if necessary) to taper off antidepressants and other drugs that they are currently taken and that cannot be taken along with duloxetine therapy. Patients who successfully taper off all excluded medications and continue to meet all of the inclusion criteria (and no exclusion criteria) at Baseline/Randomization (Visit 1) will start treatment with duloxetine as indicated below and will undergo serial comprehensive assessment with questionnaires and QST. Patients will receive 7 weeks of duloxetine (1 week of 30 mg/d, 4 weeks of 60 mg/d, and 2 weeks of 30 mg/d). QST and questionnaires will be completed prior to initiation of treatment and after 5 weeks of treatment, before reduction in dose to 30 mg/d. Patients who are tolerating duloxetine well, want to continue therapy using commercial supply, and do not want to taper off duloxetine will not be required to take the final 2 weeks of 30 mg/d.

The duration of participation in this study for cases with chronic pain will be 5-11 weeks, depending on the time required for patients to taper off excluded medications and depending on if patients wish to remain on commercial duloxetine following assessment #2. This study will randomize approximately 84 patients with chronic pain.

Control subjects (n=48) who meet all eligibility criteria but who have average pain 0-1 on a 10 point scale will undergo assessment with questionnaires and QST at a single timepoint.

In order to account for treatment heterogeneity, for both the case and control cohorts subjects will be enrolled in equal numbers into the following treatment "bins": (1) surgery +/- radiation therapy, (2) surgery and chemotherapy +/- radiation therapy, (3) surgery and endocrine therapy +/- radiation therapy, (4) surgery, chemotherapy, and endocrine therapy +/- radiation therapy.

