As an illustration of the method we fitted a binary centrality status (central vs. non-central) model (a mixture of two different latent linear regression models specific for the centrality class) to cross-sectional pain severity data on 199 breast cancer patients from an unpublished cross-sectional study we conducted on breast cancer survivors 1-3 years following diagnosis. PainDETECT, age, BMI, HADS depression and anxiety, sleep disturbance, fatigue, Perceived Stress Scale, and treatment bin (listed in Figure 4) were used as explanatory phenotype variables. The model resulted in identification of two clusters (cluster 1: 64% of patients; cluster 2: 36%) of breast cancer patients defined by dissimilar regression relationships between pain and phenotype and clinical variables. Cluster 2 is characterized by persistently higher levels of pain (Figure 5). Age, BMI and fatigue are significant variables in Cluster 1 while neuropathic pain and depression mark Cluster 2 regression. While in the data analysis we will favor continuous characterization of centrality, this binary model is used as a source of information for the power analysis below. Using the AIC criterion, the two-cluster model is significantly better than the homogeneous patient population (one regression, no latent heterogeneity explained by centrality). We note that treatment was not significant ($p=0.39$), in line with our hypothesis of common pain mechanism regardless of the type of insult.

Analysis. The planned sample size for Aim 1 is 132 (84 cases and 48 controls). For Aim 2, latent dichotomous pain centrality status will be hypothesized and regressed on explanatory variables including the ones involved in the CNS pain regulation. We will assume that the causality of the effect of the centrality block of variables on the Duloxetine (DLX) treatment outcome will follow through the centrality status. In addition to the random effect representing the interaction between the drug effect and the

[figure not shown]

Fig. 5. Clustering of 199 BCS using a mixture of 2 (pain ~ phenotype + treatment + demographics) regression models. Red high pain latent cluster is loosely identified with predicted centralized pain classification, and the blue cluster with non-centralized. Note that none of the phenotype variables taken alone serves as a particularly good surrogate for the classification, and the mixture approach that borrows strength across various phenotypes is essential.

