central status, subject specific random intercept will be introduced to model correlation due to repeated measurements. A generalized linear mixed model will be used with the two response variables (self-report pain questionnaires and experimental pain testing scores). The form of the link function and variable transformations will be determined based on the data using AIC criteria. A full likelihood model-based approach will be used to fit the model. Hypotheses will be tested by the likelihood ratio test. A clinically relevant response is defined as 50% reduction in pain within the patient. The following effects are hypothesized based on our pilot studies: Central patients will constitute approximately 30% of the breast cancer population; 10% of non-central patients are hypothesized to show clinically relevant improvement under DLX while the rate of at least 70% is hypothesized in the central group. Overall, this leads to the expected 28% response rate. Placebo effects in this kind of studies are expected not to exceed 3%. Conservatively we would be looking to detect improvement over twice the expected placebo rate (6%). Using a two-sided test for the proportion of improvement vs. 6% at $\alpha=0.05$ we will have the power of 81% with 21 patients in each "bin" (total of 84 patients).

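### With one off-drug and one on-drug visit per case, the drug-by-centrality term is a visit-by-centrality term, and it points to duloxetine only under an assumption the plan neither supports nor can test

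*Combined protocol and SAP*

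**What the plan says.** Section 4.0 records the change of design: "Therefore the study team decided to revise the study design and convert it to a single-arm open label trial". It states that the objectives are unchanged and gives one reason: "The placebo effect should be equally distributed across participants with and without centralized pain, and therefore should not influence the assessment of predictors". The summary of Amendment 7 gives the same reason.

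Objective 2 in Section 3.0 is: "To identify predictors of response to the primarily centrally-acting analgesic duloxetine in breast cancer survivors with chronic treatment-emergent pain".

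For cases, Section 5.1 sets two outcome assessments: "QST and questionnaires will be completed prior to initiation of treatment and after 5 weeks of treatment, before reduction in dose to 30 mg/d". The Section 8.0 calendar agrees, and the later telephone contact has no scheduled outcome measures. Controls "will undergo assessment with questionnaires and QST at a single timepoint"; they are nearly pain-free and untreated.

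Section 11.0 (Analysis) describes the model for Aim 2 in a sentence that a figure interrupts. It begins "In addition to the random effect representing the interaction between the drug effect and the" and continues "central status, subject specific random intercept will be introduced to model correlation due to repeated measurements". The same section defines response as a 50% within-patient reduction in pain, expects 30% of women to be central with response rates of 70% (central) and 10% (non-central), and says "Placebo effects in this kind of studies are expected not to exceed 3" per cent. It then doubles that ceiling to a 6% reference rate for the power calculation.

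**The concern.** Under a placebo crossover each woman would supply change on drug and change on placebo, so a drug-by-status term could be told apart from a visit-by-status term. In the current design nothing separates them. Whatever makes central women change differently over five weeks enters the term that the plan labels as drug effect by status.

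Section 4.0 meets this with an assumption about the placebo effect only. It gives no data, citation, check or sensitivity analysis. It does not mention regression to the mean after entry at a worst pain of 5 or more, the natural course of the pain, or change following antidepressant washout. Differential regression is foreseeable: in the pilot illustration in Section 11.0, the cluster loosely identified with centralized pain is the one with higher pain.

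At stake is how a primary objective is interpreted. The introduction expects the results to identify predictors of benefit and to bear on treatment choice. A marker of general improvement could be reported as a marker for choosing duloxetine.

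**Working it through.** **1. The plan's own figure.** Expected response is 0.30 × 0.70 + 0.70 × 0.10 = 0.28. For one bin of 21 against 6%, two-sided 0.05, the one-sample arcsine formula gives Φ[(2·asin√0.28 − 2·asin√0.06)·√21 − 1.96] = Φ(2.842 − 1.96) = 81.1%. The stated 81% is reproduced. It is power for the overall response rate against a fixed value, not for the interaction or any predictor.

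**2. Aliasing.** Write the fixed part for cases as intercept, status, visit, drug, visit × status, drug × status. Drug = 0 at Visit 1 and 1 at Visit 2 for every case, so drug = visit and drug × status = visit × status. The matrix has rank 4 of 6. Controls add no change score. In a two-period placebo crossover with four assessments (layout assumed), the rank is 6 of 6. No choice of link, random effect or AIC threshold alters this.

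**3. What the contrast estimates.** Let D be mean drug-caused change and N mean non-drug change, by status (c central, n non-central). The visit × status contrast is (Dc − Dn) + (Nc − Nn). It equals the drug interaction if and only if Nc = Nn on the scale analysed. Equality on one scale need not carry to another. With an assumed equal non-drug fall of 2 points, change SD 2, and baselines of 7.5 and 6, the 50%-reduction rates are Φ[(2 − 3.75)/2] = 19% and Φ[(2 − 3)/2] = 31%.

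**4. Size on the responder scale.** Inputs: 30% of 84 gives 25 central and 59 non-central; status treated as observed; likelihood ratio test at 0.05; no difference in drug effect.

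| Response, central v non-central | Declared predictive | Non-drug excess, all patients |
|---|---|---|
| 28% v 28% | 5.6% | 0 |
| 20% v 10% | 24% | 0.30 × 10 = 3% |
| 30% v 10% | 60% | 0.30 × 20 = 6% |
| 40% v 10% | 87% | 0.30 × 30 = 9% |

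Only the 20% v 10% row is compatible with the plan's 3% ceiling, and only if all placebo response falls in central women (0.03/0.30 = 10 points there).

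**5. Size on the change-score scale.** With an assumed change SD of 2.0 to 2.5 points, a differential non-drug change of 0.5 point is declared significant in 13–18% of trials, and one of 1 point in 38–55%.

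**6. No-drug response against the 6% reference.** Two correlated scores, rounded and clipped to 0–10, baseline at least 5, response if follow-up is at most half of baseline. The population means and SDs are assumptions. The documents do not give the five-week correlation r; Section 9.1.1 gives short-interval values only (worst pain 0.93, usual pain 0.78).

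| r | Mean/SD 4.5/2.5 to 3.5/2.8 | Mean/SD 6/2 |
|---|---|---|
| 0.93 | 0.3–0.9% | 0.0% |
| 0.8 | 4.8–8.5% | 1.0% |
| 0.7 | 9–15% | 2.4% |
| 0.6 | 14–21% | about 4% |

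Eligibility is a verbal rating and baseline is a separate BPI score. Requiring both to be at least 5 lowers the first column at r = 0.8 to 2.6–4.6%.

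**7. Not a sample-size problem.** Under the plan's 70% v 10%, a 25 v 59 comparison has more than 99.9% power. The difficulty is attribution.

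**The case against.** The strongest reply is that the plan does state an identifying assumption, and openly: placebo was dropped because accrual was failing, and equal placebo effect by centralization was offered in its place. If all non-drug change were equal by status, the contrast would be the drug interaction. This stands. A reader might infer that the design cannot identify predictors of duloxetine response under any circumstances; the documents do not support that reading. What fails is the step from an unsupported assumption about placebo alone to the conclusion that predictors are unaffected.

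Second, the model sits under exploratory analyses, the primary outcome is change in worst pain, response is a within-patient reduction, the introduction words the hypothesis as an association, and Section 13.0 says the trial studies mechanism rather than efficacy. This also stands and lowers the severity. It does not remove the point, because predicting response to duloxetine is one of two primary objectives and the subject of the title.

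Third, the larger numbers conflict with the plan's own ceiling. A reader might take the 60% or 87% as the false-finding rate to expect. They need a non-drug excess of 6% or 9% overall, two to three times the plan's 3%. That ceiling is uncited, but nothing in the documents contradicts it. A reader might equally infer that ordinary fluctuation already exceeds 6%. It does so only for some assumed populations and correlations. At the one reliability the protocol gives for worst pain it is below 1%, and with mean 6 and SD 2 it stays at or below about 4%.

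**Conclusion.** The point holds in this form. The drug-by-status term is a visit-by-status term, a structural fact that rests on no numerical assumption. Reading it as prediction of response to duloxetine requires equal non-drug change by central status on the analysed scale. The design cannot test that, and Section 4.0 asserts it for the placebo effect only. The trial can still describe which baseline features accompany improvement during open-label duloxetine; it cannot separate prognostic from drug-specific prediction.

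The size is illustrative: about 24% false declarations at 20% v 10%, about 60% at 30% v 10%, and a no-drug response from about 0% to 21%. These rest on assumed response splits, pain distributions and five-week correlations, and on status being observed, whereas the plan's status is latent. The choice of a single arm is not itself an error; it was a disclosed response to slow accrual. Severity: should be fixed.

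**What to change.** 1. Section 4.0: replace the conclusion that predictors are unaffected with a statement that equal non-drug change by central status (placebo response, regression to the mean, natural course, washout) is an untested assumption on which objective 2 depends. Restating the assumption is better than deleting it, since it is the only place the plan discloses it.
2. Section 11.0: name the term as visit (baseline, week 5) by central status.
3. Section 3.0, the synopsis and the reporting of results: word objective 2 as predictors of pain improvement during open-label duloxetine, and say that prognostic and drug-specific prediction cannot be separated.
4. Section 11.0: add a sensitivity analysis showing how large a differential non-drug change by status would account for the observed interaction, on each scale analysed.
5. Section 11.0: state that a response rate above 6% is not by itself evidence of drug activity.

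The cost is wording and one small table, with no added patients, visits or procedures. The price is a more modest claim for objective 2.

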5.0 OVERALL STUDY DESIGN AND PLAN: DESCRIPTION

5.1 Overview of Study Design

This is a single-center, single-arm, open-label study conducted at the University of Michigan's Chronic Pain and Fatigue Research Center (Figure 4). Patients with stage 0-III breast cancer who have chronic pain that developed or worsened since breast cancer diagnosis and whose worst pain is rated at least 5 on a 10 point Likert-type scale and who meet the other inclusion and exclusion criteria outlined in Sections 5.4 and 5.5 will be eligible to enroll in the study.

Patients with chronic pain (cases) who qualify for the study at Screening will begin a 1- to 4-week washout period (if necessary) to taper off antidepressants and other drugs that they are currently taken and that cannot be taken along with duloxetine therapy. Patients who successfully taper off all excluded medications and continue to meet all of the inclusion criteria (and no exclusion criteria) at Baseline/Randomization (Visit 1) will start treatment with duloxetine as indicated below and will undergo serial comprehensive assessment with questionnaires and QST. Patients will receive 7 weeks of duloxetine (1 week of 30 mg/d, 4 weeks of 60 mg/d, and 2 weeks of 30 mg/d). QST and questionnaires will be completed prior to initiation of treatment and after 5 weeks of treatment, before reduction in dose to 30 mg/d. Patients who are tolerating duloxetine well, want to continue therapy using commercial supply, and do not want to taper off duloxetine will not be required to take the final 2 weeks of 30 mg/d.

The duration of participation in this study for cases with chronic pain will be 5-11 weeks, depending on the time required for patients to taper off excluded medications and depending on if patients wish to remain on commercial duloxetine following assessment #2. This study will randomize approximately 84 patients with chronic pain.

Control subjects (n=48) who meet all eligibility criteria but who have average pain 0-1 on a 10 point scale will undergo assessment with questionnaires and QST at a single timepoint.

In order to account for treatment heterogeneity, for both the case and control cohorts subjects will be enrolled in equal numbers into the following treatment "bins": (1) surgery +/- radiation therapy, (2) surgery and chemotherapy +/- radiation therapy, (3) surgery and endocrine therapy +/- radiation therapy, (4) surgery, chemotherapy, and endocrine therapy +/- radiation therapy.

5.2 Schema

[figure not shown]

Figure 4. Schema of clinical trial design. All subjects could have received radiation therapy. Chemo: chemotherapy, ET: endocrine therapy.

5.3 Recruitment and Screening

Approximately 84 patients with chronic pain will be enrolled. Female outpatients, age ≥ 25 , who have chronic pain of at least 3 months duration that has developed or worsened since breast cancer diagnosis, and whose worst pain is rated at least 5 on a 0-10 scale, will be eligible for enrollment in this study. Subjects will be recruited from the Breast Oncology Clinics at the University of Michigan Comprehensive Cancer Center and from the Pain Clinics at the University of Michigan. Since many patients with chronic pain are treated in the Lymphedema Clinic (Occupational Therapy), the occupational therapists will be contacted in order to identify symptomatic and therefore potentially eligible patients in their clinics. In addition, 48 controls without chronic pain who otherwise meet the following eligibility criteria (inclusion #1-3, exclusion #1, 2, 4, 5, worst pain score 0-1, and not currently on medication for pain) will be recruited and will undergo baseline evaluation.

5.4 Inclusion Criteria

To be eligible to participate in this study as a case, patients must meet the following criteria:

1. Written informed consent obtained from the patient before the initiation of any study-specific procedures
2. Female patients at least 25 years of age
3. Diagnosis of stage 0-III breast cancer within 12 years prior to enrollment. All indicated surgery, chemotherapy, and/or radiation therapy must have been completed at least 12 weeks prior to enrollment. Concomitant endocrine therapy and trastuzumab are permitted.
4. Pain that developed or worsened since breast cancer diagnosis and is not due to identifiable traumatic event or fracture
5. Patient-reported worst pain score between 5 and 10 (inclusive) on a 0-10 scale (assessed verbally)
6. Female patients must be at least 1 year postmenopausal or surgically sterile; or must agree to use a medically acceptable form of contraception
7. Willing to withdraw from selective serotonin reuptake inhibitors and tricyclic antidepressants prior to treatment initiation
8. Patients who are currently taking NSAIDs and/or opioid pain medications must remain on a stable dosage throughout the duration of the study

5.5 Exclusion Criteria

Patients who meet any of the following criteria will not be eligible to participate in the study as a case:

1. Prior use of duloxetine or milnacipran.
2. Prior use of venlafaxine specifically for treatment of pain (prior use for treatment of other indications, such as hot flashes, is permitted)
3. Patients must not be taking any contraindicated medications listed on the duloxetine package insert including the following: phenothiazines, propafenone, flecanide, linezolid, or anticoagulation medication (e.g., heparin, warfarin); treatment with MAO inhibitor within 14 days prior to registration
4. Thumbnail abnormalities on either hand (such as due to chemotherapy or trauma, or artificial nails) that are likely to alter pain perception during testing
5. Peripheral sensory neuropathy at the thumbs bilaterally that interferes with function and/or activities of daily living
6. Significant risk of suicide based on the Investigator's judgment
7. History or behavior that would, in the Investigator's judgment, prohibit compliance for the duration of the study.
8. History of alcohol or other substance abuse or dependence within the year prior to registration
9. Known chronic liver disease, end stage renal disease, or creatinine clearance <30 mL/min as defined by Cockcroft-Gault equation
10. Uncontrolled narrow-angle glaucoma.
11. Clinically significant coagulation disorder
12. Pregnant or breast-feeding. Urine pregnancy test will be assessed at the baseline visit in women of child-bearing potential with chronic pain.
13. Unable to take oral medications or any medical condition that would interfere with the absorption of study medication capsules.

Controls are patients without chronic pain who otherwise meet the following eligibility criteria (inclusion #1-3, exclusion #1, 2, 4, 5, worst pain score 0-1, and not currently on medication for pain)

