5.6 Replacement Procedures

Patients with chronic pain who prematurely discontinue from this study after randomization may be replaced to obtain 84 completers.

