5.7 Removal of Patients from Therapy

A premature discontinuation will occur when a patient who signed the informed consent form ceases participation in the study, regardless of the circumstances, before the completion of the protocol. Patients can be prematurely discontinued from the study for one of the following reasons:

- Failure to meet inclusion/exclusion criteria
- Adverse event (AE)
- Insufficient therapeutic response
- Discontinuation of study medication for more than 7 days
- Protocol violation, including lack of compliance
- Withdrawal of consent

- Other reasons, such as administrative reasons or pregnancy

All patients who prematurely discontinue from the study, regardless of the cause, should undergo a final assessment.

- Those subjects who are taking medication from the 4 week supply at the time of study discontinuation will be asked to undergo in person evaluation with QST and questionnaire completion). At that in person visit they will receive the 2 week supply of medication to taper off the study drug, will be called by the study team 1-2 weeks later to assess AEs, and will be given a stamped envelope in which to return the medication bottle. If they are not willing to return to clinic they will undergo the Final Evaluation (phone visit) and will be mailed the 2 week supply of medication to taper off the study drug. Subjects will be required to return all study drug and medication bottles.
- Those subjects who are taking medication from either the 1 week or 2 week supply at the time of study discontinuation will undergo the Final Evaluation (phone visit). No taper is required. Patients will be required to return all randomized study drug.

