7.0 Concomitant Therapy

7.1 Allowable Concomitant Therapy

The following medications/therapies will be allowed for patient use during this study:

- Serotonin (*5-hydroxytryptamine*) agonists (triptans), eg, rizatriptan (Maxalt), sumatriptan (Imitrex), zolmitriptan (Zomig)
 - The use of 5-hydroxytryptamine receptor agonists (triptans) is allowed in this study; however, serotonin syndrome may occur with agents that inhibit serotonin reuptake, including duloxetine, particularly with concomitant use of serotonergic drugs (including triptans) and with drugs that impair metabolism of serotonin (including monoamine oxidase inhibitors). Serotonin syndrome may include mental status changes (eg, agitation, hallucinations, coma), autonomic instability (eg, tachycardia, labile blood pressure, hyperthermia), neuromuscular aberrations (eg, hyperreflexia, incoordination), and/or gastrointestinal symptoms (eg, nausea, vomiting, diarrhea). Careful observation of the patient is advised if triptans are used as concomitant therapy

- Epinephrine and other adrenergic agents, e.g., epinephrine (EpiPen), pseudoephedrine (Sudafed)
 - Because duloxetine increases noradrenergic activity, epinephrine (EpiPen) should only be used in the event of a severe allergic reaction (anaphylaxis). Caution should be exercised with the use of local anesthetics that contain epinephrine, nasal decongestants that contain pseudoephedrine (e.g., Sudafed), and herbal supplements that contain stimulants (e.g., bitter orange), as these may increase heart rate or blood pressure
- Nonbenzodiazepine hypnotics, eg, zaleplon (Sonata), zolpidem (Ambien)
 - Zaleplon (Sonata) will be allowed as a first-tier selection for those patients requiring treatment of insomnia. Antihistamines and chloral hydrate are also allowed
- Nonsteroidal anti-inflammatory agents, eg, ibuprofen (Motrin), naproxen (Naprosyn), ketorolac (Toradol)
- Physical modalities
 - Modalities commonly employed during routine physical therapy, chiropractic manipulation, and/or massage therapy are allowed provided they do not involve the use of injected medications

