7.2 Prohibited Concomitant Therapy

The following medications/therapies will be prohibited throughout the course of this study:

- Antidepressants, eg, escitalopram (Lexapro), venlafaxine (Effexor), milnacipran (Savella), fluoxetine (Prozac), bupropion (Wellbutrin), nortriptyline (Pamelor), monoamine oxidase (MAO) inhibitors (Parnate)
- Phenothiazines
- Propafenone and flecanide
- Antiepileptics, e.g., phenytoin (Dilantin), topiramate (Topamax), carbamazepine (Tegretol), levetiracetam (Keppra), tiagabine (Gabitril)

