Baseline (Visit 1) will be conducted 0 to 4 weeks (depending on the patient's washout period) after Screening to determine whether the patient is eligible to continue into the study treatment period. Those patients who do not need to discontinue any medications can proceed directly to Baseline (Visit 1). Patients who continue to meet inclusion criteria (and no exclusion criteria) will initiate treatment with duloxetine following baseline assessment. At this visit, patients will be given prescription bottles containing (1) a 1-week supply of study drug for the escalation period and (2) a 4-week supply of study drug for the treatment period, as well as the Period 1 medication log.

At Baseline (Visit 1) the following procedures will be completed:

- Review inclusion and exclusion criteria
- Assess and record baseline AEs
- Inquire as to any changes in physical symptoms, sleep and/or mood (to include suicidal ideation) (not required if screening and baseline are performed on the same day)
- Record concomitant medications/therapies on concomitant medication form
- Measure vital signs, including temperature, weight, height, sitting BP, and heart rate, and record values (not required if screening and baseline are performed on the same day)
- Perform urine pregnancy test in women of childbearing potential (not controls)
- Complete the following outcome assessments:
 - Evaluation of pressure pain threshold
 - Patient-reported outcome assessments:
 - Brief Pain Inventory (BPI)
 - Michigan Body Map and Symptom Severity Scale
 - PainDETECT
 - FACT/GOG-NTX subscale
 - Evaluation of CPM
 - Patient-reported outcome assessments
 - PROMIS (Fatigue-SF)
 - PROMIS (Sleep Disturbance-SF)
 - PROMIS (Physical Function-SF)

- Hospital Anxiety and Depression Scale (HADS)
- Multiple Ability Self-Report Questionnaire (MASQ)

(Control subjects will not participate in any additional study activities listed below.)

- Dispense the prescription bottles containing study drug for the first 5 weeks of the first treatment period (7 days of dose escalation and 28 days of full-dose treatment) and review dosing instructions. The subject should take the medication in the morning starting the morning after the baseline visit at approximately the same time each day. She should record when she took the medication on the provided Period 1 medication log. On the study visit days she should take her dose prior to the visit.

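### Linezolid and anticoagulants are barred at entry as contraindicated with duloxetine, but are missing from the list of therapies prohibited during the study (7.2)

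*Combined protocol and SAP*

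**What the plan says.** Exclusion #3 (5.5) requires that cases not be taking drugs contraindicated on the duloxetine package insert. It names phenothiazines, propafenone, flecainide and "linezolid, or anticoagulation medication (e.g., heparin, warfarin"), and adds MAO inhibitors within 14 days before registration. The named drugs are given as examples of the insert's list.

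Two sections govern drugs taken on study. Section 7.1 opens with "The following medications/therapies will be allowed for patient use during this study", and 7.2 with "The following medications/therapies will be prohibited throughout the course of this study". Section 7.2 has four entries: antidepressants (with MAO inhibitors among the examples), phenothiazines, propafenone with flecainide, and antiepileptics.

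On timing, the schedule in 8.0 marks the inclusion/exclusion review at Screening and Visit 1 only. Section 8.2 then says: "The subject should take the medication in the morning starting the morning after the baseline visit". Concomitant medications are recorded at Visit 2 and reviewed at the closing phone call. Neither entry says what to do if a contraindicated drug has been started.

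Section 5.7 sets out removal from therapy: "Patients can be prematurely discontinued from the study for one of the following reasons". The reasons include failing the entry criteria, an adverse event, and "Protocol violation, including lack of compliance".

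**The concern.** An exclusion criterion decides who may enter. The prohibited list decides what may happen afterwards. When a drug is barred at entry because it is contraindicated with the study drug, one expects it on both lists, because the reason for the bar lasts as long as dosing does. Here the on-study list repeats most of the entry list but not all of it, so a reader cannot tell whether the two omissions were deliberate.

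What is at stake is patient safety and a clear instruction for staff. A coordinator who tells a case at Visit 1 which drugs to avoid, or who reviews the medication form at Visit 2, would naturally work from 7.2, and 7.2 is silent on these two. The point concerns the 84 planned cases only. Controls take no duloxetine, and exclusion #3 is not applied to them.

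**Working it through.** The plan gives no figure to reproduce. The check is an item-by-item comparison, followed by a search for any other rule.

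**Step 1. Items named in exclusion #3, set against the on-study lists.**

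| Item in exclusion #3 | In 7.2 (prohibited)? | In 7.1 (allowed)? |
|---|---|---|
| Phenothiazines | Yes | No |
| Propafenone | Yes | No |
| Flecainide | Yes | No |
| MAO inhibitors | Yes, under antidepressants | No |
| Linezolid | No | No |
| Anticoagulants (heparin, warfarin) | No | No |

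Items named: 6. Carried into 7.2: 4, which is 4/6 = 67%. Missing: 6 − 4 = 2, which is 2/6 = 33%.

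Section 7.1 has five entries: triptans, adrenergic agents, nonbenzodiazepine hypnotics, NSAIDs and physical modalities. None lists either drug as allowed. Its triptan entry mentions MAO inhibitors, but only in a warning. Section 7.1 does not say that unlisted drugs are barred, so silence there settles nothing.

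**Step 2. Any other mention.** Exclusion #3 is the only rule in the protocol text that names linezolid or anticoagulants.

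**Step 3. Does exclusion #3 itself run on after entry?** Its heading concerns eligibility to participate as a case, and the scheduled reviews stop at Visit 1. Where the authors want an entry criterion to continue, they say so: inclusion #8 requires stable NSAID and opioid dosing for the whole study. Exclusion #3 has no such wording. The washout text in 5.1, 6.4 and 8.2 applies before treatment starts.

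**Step 4. The period left uncovered.** Visit 1 supplies 7 + 28 = 35 days of study drug. Visit 2 may be up to 4 days early, so the next scheduled visit is roughly 35 − 4 = 31 to 35 days after the last eligibility review. With the 14-day taper, exposure can reach 35 + 14 = 49 days.

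**Step 5. Indirect cover.**
- 5.7 lists failure to meet the entry criteria as a reason for discontinuation, but it is discretionary and names no drug.
- 10.1 counts concurrent disease arising after study start as an adverse event, and an adverse event is a separate reason in 5.7.
- Exclusion #11 covers a clinically significant coagulation disorder.
- The duloxetine prescribing highlights are an appendix, but no text turns them into an on-study rule.
- 7.2 names MAO inhibitors. The documents do not say whether linezolid should be read into that class, and anticoagulants would be uncovered either way.

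None of these is an explicit prohibition.

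**The case against.** The best reply is that the omission changes little in practice. A new illness that calls for linezolid or an anticoagulant would normally be recorded as an adverse event, and 5.7 then lets the investigator stop treatment. Failing an entry criterion is also listed in 5.7, which covers any consented patient until the protocol is completed, so exclusion #3 can be read as continuing. Section 5.1 speaks of drugs that cannot be taken along with duloxetine, so the intent is not in doubt. The protocol also rests the contraindication on a package insert whose text is not in the available documents, so the size of the risk cannot be judged from them.

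Much of this stands. It shows that the practical gap is small and that the investigator has a route to act. It does not supply the missing rule. Each route depends on a judgment after the drug has been started, whereas 7.2 exists to tell staff and patients beforehand. Use that does not follow a new illness, such as a preventive anticoagulant, need not produce an adverse event at all.

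A reader might infer that starting a 7.2 drug forces a case off treatment while starting linezolid or an anticoagulant does not. The documents do not support that. A protocol violation and a failure of the entry criteria stand in the same list in 5.7, under the same permissive wording, so neither makes removal automatic. A reader might also infer that exclusion #3 treats all six items identically. It does not: MAO inhibitors carry a 14-day look-back, and the others have no time window.

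**Conclusion.** The point holds as a small safety and consistency gap. The only on-study prohibited list omits 2 of the 6 items that the protocol itself names as contraindicated at entry, so following 7.2 as written lets a case start either drug on duloxetine without breaking an explicit on-study prohibition. This rests on reading 5.5 as an entry rule, which the heading, the visit schedule and the contrast with inclusion #8 favour, although an ongoing reading is arguable.

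The documents give no rate of on-study use, so the number of cases affected cannot be estimated. No endpoint, error rate, power or sample-size figure is affected.

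Two neighbouring questions should not be folded in. For a case who stops during the 4-week supply and attends in person, 5.7 says "they will receive the 2 week supply of medication to taper off the study drug". Whether that should apply when the reason is a contraindicated drug is a fair question, but it arises equally for a phenothiazine and is not caused by this omission. Likewise, 6.4 first describes washout in terms of contraindicated drugs while antiepileptics are barred only in 7.2. That is a wording matter, because the next sentence of 6.4 and the screening text in 8.2 already require withdrawal from all excluded drugs.

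**What to change.** Either of two edits to 7.2 is enough:

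- add linezolid and anticoagulation medication (heparin and warfarin as examples) as entries; or
- state that every drug covered by exclusion #3 is prohibited while the case is on duloxetine.

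The second is more robust, because exclusion #3 refers to the package insert and gives its drugs as examples.

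A case who comes to need one of these drugs should be handled under 5.7 in the same way as for any other 7.2 drug. A separate automatic-removal rule for these two alone would create a new inconsistency with the rest of the list.

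The cost is one or two lines of text and an occasional extra discontinuation. Section 5.6 already provides that cases who stop early "may be replaced to obtain 84 completers". The analysis needs no change.
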